23.2.1.8 Conversion from cCH to eCH

Conversion is measured as ≥ 12 consecutive weeks with 0 attacks. For a participant to experience a conversion from cCH to eCH the following criteria must be fulfilled:

- The series of weeks should start with a week with 0 attacks
- The series of weeks should end with a week with 0 attacks
- At least 50% of the weeks should be observed (corresponding to 7 weeks)
- The series should consist of at least 13 consecutive weeks with 0 attacks or missing data fulfilling the above criteria.

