
Primary Objective
 
• To evaluate the long-term safety and tolerability of eptinezumab in patients with cCH	
• Endpoints for the primary objective:
– adverse events– absolute values and changes from baseline in clinical safety laboratory test values, vital signs, weight, and electrocardiogram (ECG) parameter values– potentially clinically significant (PCS) clinical safety laboratory test values, vital signs, weight changes, and ECG parameter values– development of specific anti-eptinezumab antibodies (ADA), including neutralizing antibodies (NAbs)– Columbia-Suicide Severity Rating Scale (C-SSRS) score

Secondary Objectives

- To evaluate the efficacy of eptinezumab in patients with cCH

- Endpoints for the secondary objective (efficacy):
 - Conversion from cCH to episodic cluster headache (Week 0 to Week 48): Number of patients with no cluster headache attacks for ≥ 3 consecutive months (≥ 13 consecutive weeks)
 - Change from baseline in weekly number of times an abortive therapy (oxygen and/or triptans) was used (calculated for each infusion with eptinezumab, taking the average across the first 4 weeks after the infusion)
 - Change from baseline in the average number of weekly attacks (calculated for each infusion with eptinezumab, taking the average across the first 4 weeks after the infusion)
 - Change from baseline in the 5-point self-rating pain severity scale (calculated for each infusion with eptinezumab, taking the average across the first 4 weeks after the infusion)
 - Response: $\geq 30\%$ reduction in number of weekly attacks (calculated for each infusion with eptinezumab, based on the average across the first 4 weeks after the infusion)
 - Response: $\geq 50\%$ reduction in number of weekly attacks (calculated for each infusion with eptinezumab, based on the average across the first 4 weeks after the infusion)
 - cCH remission (Week 0 to Week 48): Number of patients with no cluster headache attacks for ≥ 1 month (5 consecutive weeks)
 - cCH remission (Week 0 to Week 12): Number of patients with no cluster headache attacks for ≥ 1 month (5 consecutive weeks between the first and second infusion)
 - cCH remission (Week 12 to Week 24): Number of patients with no cluster headache attacks for ≥ 1 month (5 consecutive weeks between the second and third infusion)

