3.1.2 Chronic cluster headache

- A. Attacks fulfilling criteria for 3.1 Cluster headache and criterion B below
- B. Occurring without a remission period, or with remissions lasting <3 months, for at least 1 year.

Chronic cluster headache may arise de novo (referred to as primary cCH) or evolve from episodic cluster headache (secondary cCH). In some patients change occurs from cCH to episodic cluster headache.⁴

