Secondary Objectives 
 To evaluate the efficacy of eptinezumab in participants with cCH 	
 Secondary endpoints: 
 - Change from Baseline in the number of weekly attacks (Weeks 1-4 and Weeks 1-2) - Change from Baseline in the number of monthly attacks (Months 1-12) - Conversion from cCH to episodic cluster headache (eCH): no cluster headache attacks for ≥ 3 consecutive months (≥ 12 consecutive weeks) (Weeks 1-48) - Change from Baseline in the weekly number of times an abortive therapy (oxygen and/or triptans where it will count as 2 times in case oxygen and triptans were used for the same attack) was used (Weeks 1, 2, 3, 4, 13, 14, 15, 16, 25, 26, 27, 28, 37, 38, 39, 40) - Change from Baseline in the weekly number of times an abortive therapy (oxygen) was used (Weeks 1, 2, 3, 4, 13, 14, 15, 16, 25, 26, 27, 28, 37, 38, 39, 40) - Change from Baseline in the weekly number of times an abortive therapy (triptans) was used (Weeks 1, 2, 3, 4, 13, 14, 15, 16, 25, 26, 27, 28, 37, 38, 39, 40) - Change from Baseline in the number of weekly attacks (Weeks 1, 2, 3, 4, 13, 14, 15, 16, 25, 26, 27, 28, 37, 38, 39, 40) - Change from Baseline in the average attack related daily pain (including days with no attacks), as assessed using the 5-point self-rating pain severity scale (Weeks 1, 2, 3, 4, 13, 14, 15, 16, 25, 26, 27, 28, 37, 38, 39, 40) - Response: $\geq 30\%$ reduction from Baseline in the number of weekly attacks (Weeks 1, 2, 3, 4, 13, 14, 15, 16, 25, 26, 27, 28, 37, 38, 39, 40) - Response: $\geq 50\%$ reduction from Baseline in the number of weekly attacks (Weeks 1, 2, 3, 4, 13, 14, 15, 16, 25, 26, 27, 28, 37, 38, 39, 40) - Response: $\geq 75\%$ reduction from Baseline in the number of weekly attacks (Weeks 1, 2, 3, 4, 13, 14, 15, 16, 25, 26, 27, 28, 37, 38, 39, 40) - cCH remission: no cluster headache attacks for ≥ 1 month (≥ 4 consecutive weeks) (Weeks 1-48) - cCH remission: no cluster headache attacks for ≥ 1 month (≥ 4 consecutive weeks) (Weeks 1-12, 13-24, 25-36, 37-48) - Use of transitional treatment (Weeks 1-48)

Objectives	Endpoints

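### SAP 23.2.1.8 sets conversion at both 12 and 13 weeks, chapter 22 does not list the shorter 12- and 4-week wording, and short diary weeks with recorded attacks can pass as missing inside an attack-free series

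*SAP*

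**What the plan says.** **Conversion, SAP.** Section 23.2.1.8 opens with a threshold of at least "12 consecutive weeks with 0 attacks. For a participant to experience a conversion from cCH to eCH the following criteria must be fulfilled". The list that follows includes "At least 50% of the weeks should be observed (corresponding to 7 weeks") and closes with "The series should consist of at least 13 consecutive weeks with 0 attacks or missing data fulfilling the above criteria". Panel 2 in chapter 5 gives at least "12 consecutive weeks) (Weeks 1-48"), and 23.1 repeats it.

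**Conversion, protocol.** Section 2, Panel 3 requires at least "13 consecutive weeks".

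**Remission.** For the first infusion interval the protocol asks for "5 consecutive weeks between the first and second infusion", and it uses 5 weeks for the other periods too. SAP Panel 2 has at least "4 consecutive weeks) (Weeks 1-12, 13-24, 25-36, 37-48"). Sections 23.1 and 23.2.1.9 also use 4, and 23.2.1.9 allows one missing week.

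**Disclosure.** SAP chapter 22 itemises the FAS change, the added endpoints, the estimands and the log-transformed baseline. On existing endpoints it says only that their phrasing was clarified and the names of endpoint types changed. It names neither 13 to 12 nor 5 to 4.

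**Missing weeks.** Under SAP 23.2.1.3, a week in a daily-entry period with 3 or fewer completed days has its weekly observation set to missing.

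**Data set.** SAP 13.5.4 applies the long-term estimand's handling to attack-based endpoints, and chapter 6 gives DPS3 to analyses of eDiary data. Section 13.5.6.3 sends endpoints such as these to the chapter 7 descriptive statistics, which chapter 6 gives to DPS1.

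**The concern.** Conversion and remission are secondary endpoints reported descriptively, with no formal testing, so the count is the whole result. If the definition can be programmed in two ways, the reported number depends on which line the programmer follows.

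The shorter lengths make both endpoints easier to reach in an uncontrolled, open-label trial. Chapter 22 does not tell a reader that the numbers differ from the protocol's.

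Both endpoints claim the absence of attacks. A rule that turns a poorly completed week into a missing one, and then tolerates missing weeks, can let a participant who recorded attacks be reported as free of them.

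**Working it through.** **1. The plan's own figure.** Minimum observed weeks = 50% of the series length L, rounded up.
- L = 13: 0.5 × 13 = 6.5, rounded up to 7. This reproduces the SAP's 7, and leaves at most 13 − 7 = 6 missing.
- L = 12: 0.5 × 12 = 6. This does not reproduce it.

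The criteria list in 23.2.1.8 is consistent with 13 throughout; only its opening sentence says 12.

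**2. A participant on the boundary.** Suppose Weeks 5–16 are all observed with 0 attacks and every other week has attacks. The run is 12 weeks. By the opening sentence, Panel 2 and 23.1, 12 ≥ 12, so converted. By the criteria list, 12 < 13, so not converted.

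**3. Lengths side by side.**

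| Source | Conversion | Remission |
|---|---|---|
| Protocol section 2, Panel 3 | ≥13 | 5 |
| SAP Panel 2 and 23.1 | ≥12 | ≥4 |
| SAP 23.2.1.8, opening sentence | ≥12 | – |
| SAP 23.2.1.8, criteria | ≥13, 7 observed | – |
| SAP 23.2.1.9 | – | ≥4, at most 1 missing |

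The 12 and 4 match the 28-day month of SAP 3.4: 3 × 28 = 84 days = 12 weeks, and 28 days = 4 weeks. The protocol's lengths are 13 × 7 = 91 days and 5 × 7 = 35 days. The 28-day month may explain the change but does not disclose it.

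**4. Recorded attacks in short weeks.** Daily entry applies to Weeks 1–4, 13–16, 25–28 and 37–40. A series must start and end on an observed zero week, so a missing week can only be interior.
- There are 48 − 13 + 1 = 36 possible 13-week series. Each contains 4 or 5 daily-entry weeks, 3 or 4 of them interior.
- Limit case for a 13-week series: Weeks 5–17, with three completed days in each of Weeks 13–16, two attacks on each of those days, and zero attacks in the other weeks. Weeks 13–16 become missing, leaving 13 − 4 = 9 observed, and 9 ≥ 7. The criteria are met despite 4 × 3 = 12 days carrying 24 recorded attacks.
- Control: four completed days with one attack in total give 7 × 1/4 = 1.75, an observed non-zero week, and the series breaks.
- Remission: Weeks 1–4 with three completed days and 9 attacks in Week 2, and the other three weeks zero. One week is missing and three are observed zeros, so 23.2.1.9 is met. Only four weeks are involved, so the protocol's 5 is not met.

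This route does not depend on the data point set. It arises only in daily-entry weeks.

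**5. Data set.** Take a daily-entry week with no attacks on days 1–4, transitional treatment on day 4 and two attacks on each of days 5–7. On DPS1 the score is 6. On DPS3, days 5–7 are removed, and the four zero days prorate to 7 × 0/4 = 0. The choice of set can therefore decide whether a series survives.

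**The case against.** **The conversion threshold has not really moved.** The mandatory list in 23.2.1.8 keeps the protocol's 13 and the matching 7. A reader might infer that the SAP dropped the protocol definition; the documents do not support that. The departure exists only if the opening sentence, Panel 2 and 23.1 govern. This stands, and it points to correcting the 12s. The contradiction remains, and remission has changed to 4 throughout.

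**Chapter 22 does signal a change.** It says endpoint phrasing was revised, and the protocol itself reports monthly attacks by 4-week interval. True, but a shorter required run is not phrasing. The appeal to the diagnostic criterion ("Occurring without a remission period, or with remissions lasting <3 months, for at least 1 year") is limited. If those are calendar months (89–92 days for three), 84 days falls short, but for remission 35 days already exceeds any calendar month. Preferring the protocol's lengths therefore rests on conformity with the protocol.

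**The outcome for short weeks is not settled.** Section 23.1 says these endpoints fit none of its three data structures and count as a yes if the endpoint's criteria are met. It could be argued that a recorded attack defeats the endpoint whatever the weekly score. This stands in part: counting such a participant as converted is the natural reading, because nothing in 23.2.1.8 or 23.2.1.9 restores the recorded attacks, but it is not stated outright.

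**The limit case is extreme.** It needs four consecutive poorly completed weeks despite compliance checks at every contact. Agreed. That every 13-week series contains daily-entry weeks might suggest every conversion is doubtful. It is not: the rule matters only where a week has at most 3 completed days and an attack on one of them.

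**Any recorded attack should end a series, including on days removed after transitional treatment.** This is tempting but goes too far. SAP 13.5.3 and 13.5.4 use a hypothetical strategy. Readmitting excluded days only when they are unfavourable would change that strategy.

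**The data-set conflict is thin.** Section 13.5.4 and chapter 6 favour DPS3, and 13.5.6.3 may refer only to the type of summary. A cross-reference is enough.

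**Conclusion.** The 12-against-13 contradiction in SAP 23.2.1.8 is plain on the text, and so is the absence of either change of length from chapter 22. These two parts rest on no assumption. The short-week route follows from 23.2.1.3 read with 23.2.1.8 and 23.2.1.9, assuming that a week set to missing there counts as missing data in the series.

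The size is unknown. The documents give no rates of becoming attack-free, of relapse or of short diary weeks, so any percentage would rest on rates assumed from outside. What can be said is structural: the classification flips at exactly 12 weeks; up to 12 days with recorded attacks can lie inside a 13-week conversion through short weeks; and up to 3 can lie inside a remission series.

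The primary safety objective is untouched. The point should be fixed because the affected counts are the reported results and the repair is cheap.

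**What to change.** 1. Use one conversion threshold with its matching observed minimum in Panel 2, 23.1 and 23.2.1.8, preferably the protocol's 13 or more weeks with at least 7 observed. If 12 is kept, change 13 and 7 in the criteria to 12 and 6 and list the change in chapter 22.
2. For remission, use the protocol's 5 weeks, or list the change to 4 in chapter 22 and show the 5-week count alongside.
3. Add to 23.2.1.8 and 23.2.1.9 that a week set to missing under 23.2.1.3 because 3 or fewer days were completed ends the series if any attack was recorded on the completed days.
4. Add to 13.5.6.3 a cross-reference that the 13.5.4 handling (DPS3) applies to conversion and remission.
5. Do not extend item 3 to data excluded under 23.2.1.5 in the main count; at most show that as a sensitivity count.

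The cost is SAP wording, a small programming change and one extra table row if both remission lengths are shown. Item 3, and the longer thresholds, can only leave counts unchanged or lower them, because every series that qualifies under the stricter rule also qualifies under the looser one. No data collection changes.

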23.2.1.9 Remission

For a participant to be in remission for the period listed in the endpoint the following should be fulfilled:

- The series of weeks should start with a week with 0 attacks
- The series of weeks should end with a week with 0 attacks
- All observed weeks should have 0 attacks
- A maximum of 1 missing week
- The series should consist of at least 4 consecutive weeks (which should all be in the period listed in the endpoint)

23.2.2 1-year Exposure

For a participant to count as having a 1-year exposure the following should be fulfilled:

- A participant should have had 4 infusions with eptinezumab
- A participant should have been followed for at least 365 days after their first infusion.
Thus, there should be some data/contact/visit with a date that is 365 days or more after first infusion with eptinezumab

23.2.3 Country

Countries with at least 20 participants will be kept individually, and countries with less than 20 participants will be combined into one country called “other”.

23.2.4 Use of Transitional Treatment

To address the endpoint Use of transitional treatment (Weeks 1-48), use of a transitional treatment will be collected from the “Transitional and Preventive Treatment for Cluster Headache Log” and in case of no findings, a participant will get a corresponding value of 0 for number of times a transitional therapy was used.

If a participant withdraws, any transitional treatment that is collected from the form will be considered up until 48 weeks after the first IMP infusion.

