 - cCH remission (Week 24 to Week 36): Number of patients with no cluster headache attacks for ≥ 1 month (5 consecutive weeks between the third and fourth infusion)
 - cCH remission (Week 36 to Week 48): Number of patients with no cluster headache attacks for ≥ 1 month (5 consecutive weeks within the first 12 weeks after the fourth infusion)
 - Number of patients who received a transitional therapy during the Treatment Period (Week 0 to Week 48)
 - Patient Global Impression of Change (PGIC) score (assessed monthly after the first eptinezumab infusion)
 - Change from baseline in Sleep Impact Scale (SIS) domain scores (at each infusion and 4 weeks after each infusion)

Secondary Objectives (continued) 
• To evaluate the efficacy of eptinezumab in patients with cCH (continued)	
• Exploratory endpoints for the secondary objective (efficacy):
– Change from baseline in the average number of monthly attacks (per 4-week intervals after each eptinezumab infusion)– Change from baseline in the 5-point self-rating pain severity scale (taking the average across 4-week intervals after each eptinezumab infusion)– Response: $\geq 30\%$ reduction in number of monthly attacks by 4-week intervals after each eptinezumab infusion, and for each of the periods between infusions with eptinezumab, and for 12 weeks after the last eptinezumab infusion– Response: $\geq 50\%$ reduction in number of monthly attacks by 4-week intervals after each eptinezumab infusion, and for each of the periods between infusions with eptinezumab, and for 12 weeks after the last eptinezumab infusion– Response: 100% reduction in number of monthly attacks by 4-week intervals after each eptinezumab infusion, and for each of the periods between infusions with eptinezumab, and for 12 weeks after the last eptinezumab infusion– Change from baseline in monthly number of times an abortive therapy (oxygen and/or triptans) was used (per 4-week interval after each eptinezumab infusion)

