8.7 Withdrawal Visit

Three different scenarios can occur, depending on whether the patients withdraw from the study, from treatment or withdraw their consent.

Patients who withdraw from the study prior to the Completion Visit (Week 48/Visit 14), except for those who withdraw their consent, will be asked to attend a Withdrawal Visit as soon as possible and a further SFU Visit, scheduled 20 weeks (5 half-lives) after the last eptinezumab administration.

Patients who are withdrawn from the treatment prior to the Completion Visit (Week 48/Visit 14) will be given the opportunity to remain in the study at the discretion of the investigator. Patients will be expected to attend all scheduled study visits and procedures except eptinezumab administration. If patients refuse, they will be asked to attend a Withdrawal Visit as soon as possible and a further SFU Visit, scheduled 20 weeks (5 half-lives) after the last eptinezumab administration.

No new information will be collected from patients who withdraw from the study or decide to withdraw, except information collected in relation to the scheduled Withdrawal Visit and SFU Visit or needed for the follow-up of adverse events (section 10.5).

The reason for withdrawal must be recorded in the eCRF, and the investigator must ask specifically whether withdrawal was due to an adverse event.

For a patient who withdraws consent:

- if the patient withdraws consent during a site visit and then agrees to it being the final visit, the investigator will complete the visit as a Withdrawal Visit and all the data collected up to and including that visit will be used;
- if the patient withdraws consent during a telephone conversation, the investigator will ask the patient if he or she will attend a Withdrawal Visit. If the patient:
 - agrees to attend a Withdrawal Visit, all the data collected up to and including that visit will be used;
 - refuses to attend a Withdrawal Visit, the investigator should attempt to follow the patient's safety and future treatment; any information collected will only be recorded in the patient's medical records;
- if the patient explicitly requests that the patient's data collected from the time of withdrawal of consent onwards not be used, this will be respected.

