
Objectives	Endpoints
Exploratory Objective 
To explore the target engagement of eptinezumab to calcitonin gene-related peptide (CGRP)	
Exploratory endpointChange from Baseline in CGRP (CGRP-eptinezumab complex, free CGRP) at Weeks 12, 24, 36, and 48

6 Analysis Sets

The following analysis sets will be used to analyse and present the data:

- all-participants-enrolled set* (APES) – all enrolled participants
- all-participants-treated set* (APTS) - all participants in the APES who received infusion with eptinezumab
- full-analysis set* (FAS) - all participants in the APTS who have a valid assessment of the baseline number of weekly attacks and a post-baseline assessment of number of weekly attacks.

The participants and data will be classified into the analysis sets during a *Classification Meeting* according to the definitions above after the trial database has been released, but prior to the headline results meeting.

Safety analyses (including tolerability and exposure), disposition, demographics and baseline characteristics will be based on APTS.

Efficacy analyses will be based on FAS.

Three Data Point Sets (DPS) will be used for presenting the results using eDiary data:

- DPS1: All data points obtained at or after enrolment
- DPS2: All data points obtained at or after enrolment except for those following the 7-day rule after the use of transitional treatment (for details see section 23.2.4)
- DPS3: All data points obtained at or after enrolment except for those following the 7-day rule after the use of transitional treatment (see section 23.2.4) and those following the 12-week rule after withdrawal from treatment (see section 23.2.1.5)

DPS1 will be used for the descriptive statistics described in chapter 7 as well as the sensitivity analyses described in sections 13.5.9.1 and 13.5.9.2, DPS2 will be used for the short-term efficacy estimand described in section 13.5.1, and DPS3 will be used for the long-term efficacy estimand (section 13.5.3), the sensitivity analysis described in section 13.5.9.3, and analyses based on eDiary data. For more details see chapter 13.

For efficacy data not derived from the eDiary all analyses will be based on all data points obtained at or after enrolment.

7 Descriptive Statistics

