13.5.6.3 Other Efficacy Endpoints

Endpoints that are not covered by sections [13.5.6.1](#) and [13.5.6.2](#) will only be summarized descriptively as described in chapter [7](#).

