- Use of preventive medication (Weeks 1-48)

do not fit into either of the data structures in 1), 2) or 3) but will be assessed by a yes if the participant is fulfilling the criteria in the endpoint.

The ePRO data measured in connection with visits will be looked at in one way: the relevant week numbers corresponding to the visits will be considered in the analyses.

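### Early leavers with no logged transitional treatment are scored as non-users for all 48 weeks, so the descriptive 48-week proportion can be understated but not overstated

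*SAP*

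**What the plan says.** Use of transitional treatment over Weeks 1-48 is a secondary endpoint (SAP section 5, Panel 2). The protocol frames it as a count of patients given such therapy between Week 0 and Week 48 (Protocol section 2, Panel 3).

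SAP 23.2.4 takes the data from the log of transitional and preventive treatments. When the log is empty, "a participant will get a corresponding value of 0 for number of times a transitional therapy was used". For a participant who withdraws, "any transitional treatment that is collected from the form will be considered up until 48 weeks after the first IMP infusion". No minimum follow-up is required.

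SAP 23.1 says that endpoints of this kind "will be assessed by a yes if the participant is fulfilling the criteria in the endpoint", and gives no not-evaluable category. SAP section 6 adds "Efficacy analyses will be based on FAS". Under SAP 13.5.6.3 the endpoint falls among those that "will only be summarized descriptively as described in chapter" 7. The sensitivity analysis for transitional treatment (SAP 13.5.9.1) covers only the two attack-count estimands.

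On follow-up after leaving, Protocol 8.7 states: "No new information will be collected from patients who withdraw from the study or decide to withdraw". The same sentence excepts the Withdrawal Visit, the SFU Visit and follow-up of adverse events. The SFU Visit is 20 weeks after the last infusion. If consent is withdrawn, later information goes only to the medical records (Protocol 8.7 and 8.8), unless the patient agrees to a Withdrawal Visit, whose data are used.

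**The concern.** The endpoint refers to a fixed 48-week window, but a 0 can mean two things: observed for 48 weeks without use, or observed for less time with nothing logged. The rule does not separate them. The withdrawal sentence lets logged use count; it does not make unseen weeks missing or censored. Those weeks are in effect scored as free of transitional treatment.

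This happens even if leaving has nothing to do with need. It grows if those who leave are more likely to need transitional treatment, which is plausible because SAP 13.5.3 names lack of efficacy as a reason for stopping treatment.

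For response over periods, the SAP handles incomplete follow-up explicitly: SAP 23.2.1.7 sets a minimum of observed data and restricts the denominator to participants who meet it. SAP 13.5.9.3 adds last-observation and worst-case imputations for 75% response. Transitional use has neither. At stake is a descriptive percentage that a reader will naturally take as the 48-week risk of needing transitional therapy on eptinezumab.

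**Working it through.** **The plan's own figure.** Planned enrolment is 100/(1 - 0.20) = 125, as stated in SAP section 20 and Protocol 16.11. So about 25 of 125 participants may have incomplete follow-up. The two cited 12-week studies in chronic cluster headache had under 4% and about 7% withdrawal. At constant rates these give 1 - 0.96^4 = 15.1% and 1 - 0.93^4 = 25.2% over 48 weeks, either side of 20%.

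**How far recording reaches.** Concomitant medication is recorded until the SFU Visit (Protocol section 7) and is scheduled at both the Withdrawal and SFU Visits (Protocol Panel 2). I assume the log is updated on the same occasions. With the SFU Visit 20 weeks after the last infusion:

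| Last infusion | Given at week | SFU at week | Weeks to 48 left unseen |
|---|---|---|---|
| 1st | 0 | 20 | 28 |
| 2nd | 12 | 32 | 16 |
| 3rd | 24 | 44 | 4 |
| 4th | 36 | 56 | 0 |

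If consent is withdrawn or the SFU Visit is missed, recording stops at withdrawal.

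**Illustrative size.** The documents give no rate of use, so these are assumptions: true 48-week use of 20% in completers, withdrawal of 20% spread evenly over 48 weeks, and a constant hazard of first use. Take 48 weeks as the time unit, so the hazard is -ln(0.8) = 0.2231.

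*Same rate in those who leave; recording stops at withdrawal.* Their average recorded use is 1 - (1 - 0.8)/0.2231 = 0.1037. Overall: 0.8 × 0.20 + 0.2 × 0.1037 = 0.181. With exponential rather than uniform withdrawal, both hazards are 0.2231 and the figure is 0.5 × (1 - 0.8 × 0.8) = 0.180. Either way it is about 18% against a true 20%.

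*Same rate; recording runs to the SFU Visit.* A quarter of those who leave fall in each row of the table. Recorded use is 1 - 0.8^(20/48) = 0.0888, 1 - 0.8^(32/48) = 0.1382, 1 - 0.8^(44/48) = 0.1850 and 0.2000, with mean 0.1530. Overall: 0.16 + 0.2 × 0.1530 = 0.191.

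*Higher rate of use in those who leave.* The same formulas with the hazard doubled or tripled in that group give:

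| Rate in leavers | True | Reported, to SFU | Reported, to withdrawal |
|---|---|---|---|
| 1x | 20.0% | 19.1% | 18.1% |
| 2x | 23.2% | 21.6% | 19.9% |
| 3x | 25.8% | 23.8% | 21.4% |

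Over withdrawal of 15% to 25%, completers' use of 10% to 40%, rates of 1x to 3x and both recording assumptions, the shortfall runs from 0.4 to 7.4 percentage points. It is never negative.

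**Bounds without a model.** Suppose 20 of 100 completers use transitional treatment and nothing is logged for the 25 who leave. The SAP rule gives 20/125 = 16.0%. Completers alone give 20/100 = 20.0%. Counting every leaver as a user gives 45/125 = 36.0%. With 25 leavers, the largest possible shortfall is 25/125 = 20 points.

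**The case against.** The best defence is that the plan does not ignore withdrawers. Use logged at the Withdrawal or SFU Visit counts, and those who stop treatment but stay in the study remain under observation. If the SFU Visit is attended, leaving after the fourth infusion costs nothing and leaving after the third costs about 4 weeks. This stands, and it roughly halves the error. A reader might infer a relative shortfall of about 10% (18% against 20%), but that needs recording to stop at withdrawal for everyone who leaves. The documents support it only where consent is withdrawn or the SFU Visit is missed, and they do not say how often that will be.

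It is also fair that the protocol endpoint is a count, and the number of participants with recorded use is correct as such. The listings of transitional medication (SAP section 10) and of study withdrawals (SAP 8.2) let a careful reader see part of the problem. They do not correct a percentage of the FAS that is read as 48-week use.

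A tempting contrast is that treating no evidence as no event is conservative for conversion and remission but favourable here. The documents do not support so clean a contrast. Conversion accepts missing weeks within a run if at least half are observed (SAP 23.2.1.8), and remission accepts one missing week (SAP 23.2.1.9), so some missing weeks count towards success there too.

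Finally, a link between leaving and need is plausible but undocumented. Transitional therapy is allowed during treatment, so needing it does not oblige anyone to leave.

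**Conclusion.** The point holds as a limited reporting weakness. The direction is certain: unseen weeks are scored as no use, so the 48-week proportion can be too low and never too high. The size is not fixed by the documents. At 20% withdrawal and 20% true use unrelated to leaving, the shortfall is about 0.9 points with SFU data logged and about 2 points without. If the rate in leavers is three times higher, it is 2.0 and 4.3 points. These figures rest on assumed rates of use, evenly spread withdrawal, a planning allowance for withdrawal, and the log being updated at the SFU Visit.

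A reader might infer that an efficacy conclusion is biased in favour of eptinezumab. That goes too far: the trial is single-arm and open-label with no formal testing, so a descriptive proportion is affected, not a comparison or an error rate. The 20-point figure is an arithmetic ceiling, not an expectation.

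**What to change.** Keep the count of participants with recorded use. In SAP 23.2.4 and 13.5.6.3, add:

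- a Kaplan-Meier estimate at Week 48 of time from first infusion to first transitional treatment, with 95% CI, censoring at the last contact at which the log was reviewed (the SFU Visit where attended, and at most Week 48);
- the number of participants who left before Week 48 and were scored 0;
- a worst-case bound that counts those participants as users.

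The last two are needed because Kaplan-Meier assumes that censoring is independent of need. If leavers need transitional treatment more, that estimate is also too low, and the bound shows how far it could be out.

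The cost is one extra table. Start dates and time since first infusion are already in the listing in SAP section 10, and Kaplan-Meier is already planned for study withdrawal in SAP 8.2. The only new derivation is the date of last log review. The downside for the sponsor is a slightly less favourable figure.
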